12.9. Appendix 9: Liver Safety Drug Restart Guidelines

If subject meets liver chemistry stopping criteria do not restart randomized treatment unless there is a clear underlying cause for the liver stopping event other than drug-induced liver injury and:

- GSK Medical Governance approval **is granted** (as described below),
- Ethics and/or IRB approval is obtained, if required, and
- Separate consent for randomized treatment restart is signed by the subject
- If GSK Medical Governance approval to restart subject with randomized treatment **is not granted**, then subject must permanently discontinue randomized treatment and requested to continue in the study for protocol-specified follow up assessments.

Restart Following Transient Resolving Liver Stopping Events Not Related to Randomized Treatment

Restart refers to resuming randomized treatment following liver stopping events in which there is a clear underlying cause (other than DILI) of the liver event (e.g. biliary obstruction, pancreatic events, hypotension, acute viral hepatitis). Furthermore, there should be no evidence of alcoholic hepatitis or hypersensitivity, and the randomized treatment should not be associated with HLA markers of liver injury.

Approval by GSK for randomized treatment restart can be considered where:

- Investigator requests consideration for randomized treatment restart if liver chemistries have a clear underlying cause (e.g., biliary obstruction, hypotension and liver chemistries have improved to normal or are within 1.5 x baseline and ALT <3xULN).
- Restart risk factors (e.g. fever, rash, eosinophilia, or hypersensitivity, alcoholic hepatitis, possible randomized treatment-induced liver injury) or randomized treatment has an HLA genetic marker associated with liver injury (e.g. lapatinib, abacavir, amoxicillin/clavulanate) are reviewed and excluded.
- Ethics Committee or Institutional Review Board approval of randomized treatment restart must be obtained, as required.
- If restart of randomized treatment is approved by GSK Medical Governance in writing, the subject must be provided with a clear description of the possible benefits and risks of randomized treatment administration, including the possibility of recurrent, more severe liver injury or death.
- The subject must also provide signed informed consent specifically for the randomized treatment restart. Documentation of informed consent must be recorded in the study chart.
- Randomized treatment must be administered at the dose specified by GSK.
- Subjects approved by GSK Medical Governance for restarting randomized treatment must return to the clinic once a week for liver chemistry tests until stable liver

chemistries have been demonstrated and then laboratory monitoring may resume as per protocol.

- If after randomized treatment re-start, subject meets protocol-defined liver chemistry stopping criteria, follow usual stopping criteria instructions.
- PPD Medical Monitor, and the Ethics Committee or Institutional Review Board as required, must be informed of the subject's outcome following randomized treatment restart.
- PPD to be notified of any AEs, as per Section 7.4 and [Appendix 7](#).

12.10. Appendix 10: Collection of Pregnancy Information

- Investigator will collect pregnancy information on any female subject who becomes pregnant while participating in this study.
- Information will be recorded on the appropriate form and submitted to PPD within 24 hours of learning of a subject's pregnancy.
- The subject will be followed to determine the outcome of the pregnancy. The investigator will collect follow up information on mother and infant, which will be forwarded to PPD. Generally, follow-up will not be required for longer than 6 to 8 weeks beyond the estimated delivery date.
- Any termination of pregnancy will be reported, regardless of fetal status (presence or absence of anomalies) or indication for procedure.
- While pregnancy itself is not considered to be an AE or SAE, any pregnancy complication or elective termination of a pregnancy will be reported as an AE or SAE.
- A spontaneous abortion is always considered to be an SAE and will be reported as such.
- Any SAE occurring as a result of a post-study pregnancy which is considered by the investigator reasonably related to the randomized treatment, will be reported to PPD as described in [Appendix 7](#). While the investigator is not obligated to actively seek this information in former study participants, he or she may learn of an SAE through spontaneous reporting.

Any female subject who becomes pregnant while participating must permanently discontinue randomized treatment. Subjects will be asked to attend an Early Treatment Discontinuation visit and expected to attend study visits through the End of Study visit, according to the study visit schedule, unless consent is actively withdrawn.

12.11. Appendix 11: Genetic Research

Genetics – Background

Naturally occurring genetic variation may contribute to inter-individual variability in response to medicines, as well as an individual's risk of developing specific diseases. Genetic factors associated with disease characteristics may also be associated with response to therapy, and could help to explain some clinical study outcomes. For example, genetic variants associated with age-related macular degeneration (AMD) are reported to account for much of the risk for the condition [Gorin, 2012] with certain variants reported to influence treatment response [Chen, 2012]. Thus, knowledge of the genetic etiology of disease may better inform understanding of disease and the development of medicines. Additionally, genetic variability may impact the pharmacokinetics (absorption, distribution, metabolism, and elimination), or pharmacodynamics (relationship between concentration and pharmacologic effects or the time course of pharmacologic effects) of a specific medicine and/or clinical outcomes (efficacy and/or safety) observed in a clinical study.

Genetic Research Objectives and Analyses

The objectives of the genetic research are to investigate the relationship between genetic variants and:

- Response to medicine, including any treatment regimens under investigation in this study or any concomitant medicines;
- Anemia associated with CKD susceptibility, severity, and progression and related conditions

Genetic data may be generated while the study is underway or following completion of the study. Genetic evaluations may include focused candidate gene approaches and/or examination of a large number of genetic variants throughout the genome (whole genome analyses). Genetic analyses will utilize data collected in the study and will be limited to understanding the objectives highlighted above. Analyses may be performed using data from multiple clinical studies to investigate these research objectives.

Appropriate descriptive and/or statistical analysis methods will be used. A detailed description of any planned analyses will be documented in a Reporting and Analysis Plan (RAP) prior to initiation of the analysis. Planned analyses and results of genetic investigations will be reported either as part of the clinical RAP and study report, or in a separate genetics RAP and report, as appropriate.

Study Population

Any subject who is randomized in the study can participate in genetic research. Any subject who has received an allogeneic bone marrow transplant must be excluded from the genetic research.

Study Assessments and Procedures

A key component of successful genetic research is the collection of samples during clinical studies. Collection of samples, even when no *a priori* hypothesis has been identified, may enable future genetic analyses to be conducted to help understand variability in disease and medicine response.

- A 6 ml blood sample will be taken for Deoxyribonucleic acid (DNA) extraction. A blood sample is collected at the Baseline visit, after the subject has been randomized and provided informed consent for genetic research. Instructions for collection and shipping of the genetic sample are described in the laboratory manual. The DNA from the blood sample may undergo quality control analyses to confirm the integrity of the sample. If there are concerns regarding the quality of the sample, then the sample may be destroyed. The blood sample is taken on a single occasion unless a duplicate sample is required due to an inability to utilize the original sample.

The genetic sample is labelled (or “coded”) with the same study specific number used to label other samples and data in the study. This number can be traced or linked back to the subject by the investigator or site staff. Coded samples do not carry personal identifiers (such as name or social security number).

Samples will be stored securely and may be kept for up to 15 years after the last subject completes the study, or GSK may destroy the samples sooner. GSK or those working with GSK (for example, other researchers) will only use samples collected from the study for the purpose stated in this protocol and in the informed consent form. Samples may be used as part of the development of a companion diagnostic to support the GSK medicinal product.

Subjects can request their sample to be destroyed at any time.

Informed Consent

Subjects who do not wish to participate in the genetic research may still participate in the study. Informed consent for genetic research consent must be obtained prior to any blood being taken.

Subject Withdrawal from Study

If a subject who has consented to participate in genetic research withdraws from the clinical study for any reason other than being lost to follow-up, the subject will be given a choice of one of the following options concerning the genetic sample, if already collected:

- Continue to participate in the genetic research in which case the genetic DNA sample is retained
- Discontinue participation in the genetic research and destroy the genetic DNA sample

If a subject withdraws consent for genetic research or requests sample destruction for any reason, the investigator must complete the appropriate documentation to request sample destruction within the timeframe specified by GSK and maintain the documentation in the site study records.

Genotype data may be generated during the study or after completion of the study and may be analyzed during the study or stored for future analysis.

- If a subject withdraws consent for genetic research and genotype data has not been analyzed, it will not be analyzed or used for future research.
- Genetic data that has been analyzed at the time of withdrawn consent will continue to be stored and used, as appropriate.

Screen and Baseline Failures

If a sample for genetic research has been collected and it is determined that the subject does not meet the entry criteria for participation in the study, then the investigator should instruct the subject that their genetic sample will be destroyed. No forms are required to complete this process as it will be completed as part of the consent and sample reconciliation process. In this instance a sample destruction form will not be available to include in the site files.

Provision of Study Results and Confidentiality of Subject's Genetic Data

GSK may summarize the genetic research results in the clinical study report, or separately and may publish the results in scientific journals.

GSK may share genetic research data with other scientists to further scientific understanding in alignment with the informed consent. GSK does not inform the subject, family members, insurers, or employers of individual genotyping results that are not known to be relevant to the subject's medical care at the time of the study, unless required by law. This is due to the fact that the information generated from genetic studies is generally preliminary in nature, and therefore the significance and scientific validity of the results are undetermined. Further, data generated in a research laboratory may not meet regulatory requirements for inclusion in clinical care.

References

Gorin MB. Genetic insights into age-related macular degeneration: Controversies addressing risk, causality, and therapeutics. *Mol. Asp. Med.* 2012; 33: 467-486.

12.12. Appendix 12: A Sub-study of the Effect of Daprodustat Compared to rhEPO on BP in Hemodialysis Dependent Subjects with Anemia Associated with Chronic Kidney Disease who Switch from ESAs

12.12.1. Introduction and Rationale

Hypertension is one of the major risk factors associated with cardiovascular morbidity and mortality and is common in patients with advanced CKD Stages 3b through 5.

Treatment of anemia associated with CKD using ESAs has the associated risk of increased BP. ESA-induced elevation of BP often necessitates initiation of, or increases in, antihypertensive medications in patients with CKD. While SBP and DBP are both of prognostic importance, SBP is the overall best predictor of future cardiovascular risk in a hypertensive population [Peters, 2013]. Therefore, SBP was chosen as the primary endpoint in this ABPM sub-study. ABPM is being used to measure BP in this sub-study because previous studies have used this BP measurement modality in dialysis subjects to establish an association with mortality [Agarwal, 2010].

This sub-study is intended to compare daprodustat to rhEPO on BP as assessed by ABPM in dialysis-dependent subjects with anemia associated with CKD who switch from ESAs.

12.12.2. Objectives and Endpoints

Objectives	Endpoints
Primary	

 To compare daprodustat to rhEPO for effect on SBP (superiority) by ABPM in subjects receiving maintenance hemodialysis in the ABPM ITT population 	
 Change in 24 hour average SBP from baseline to end of sub-study¹ between treatment groups
Secondary	

 To assess the effect of daprodustat and rhEPO independently within treatment group on SBP, DBP and mean arterial blood pressure (MAP) by ABPM in the ABPM ITT population 	
 Change in 24 hour average SBP from baseline to end of sub-study¹ within each treatment group Change in 24 hour average DBP from baseline to end of sub-study¹ within each treatment group Change in 24 hour average MAP from baseline to end of sub-study¹ within each treatment group

 To compare the effect of daprodustat to rhEPO on DBP and MAP by ABPM in the ABPM ITT population 	
 Change in 24 hour average DBP from baseline to end of sub-study¹ between treatment groups Change in 24 hour average MAP from baseline to end of sub-study¹ between treatment groups

 To compare the effect of daprodustat to rhEPO on BP parameters in the ABPM per-protocol population 	
 Change in: 
 24 hour average SBP 24 hour average DBP 24 hour average mean arterial pressure from baseline to end of sub-study¹ between treatment groups

Objectives	Endpoints

 To assess the effect of daprodustat and rhEPO on BP parameters in the ABPM per-protocol population 	
 Change in: 
 24 hour average SBP 24 hour average DBP 24 hour average mean arterial pressure from baseline to end of sub-study¹ within each treatment group

 To compare the percentage of subjects in each treatment group requiring a change in antihypertensive medications in the ABPM ITT population 	
 Difference between treatment groups in percentage of subjects requiring no change in number or dosage of antihypertensive medications Difference between treatment groups in percentage of subjects requiring an increase in number or dosage of antihypertensive medications Difference between treatment groups in percentage of subjects requiring a decrease in number or dosage of antihypertensive medications

 To characterize the dipping pattern of sleeping BP in each treatment group in the ABPM ITT and ABPM per-protocol populations 	
 24 hour BP profile as measured by ABPM, with subjects categorized according to their sleeping BP behaviors as: 
 dippers (normal) when the reduction in the average SBP during the sleeping period was >10% to 20% of mean SBP during waking hours, extreme dippers when this reduction was >20%, non-dippers when the reduction was <10%, and reverse dippers when the mean sleep SBP was higher than the awake SBP [Bakris, 2014]

 To compare the percentage of subjects that convert from non-dipper status to dipper status between treatment groups in the ABPM ITT and ABPM per-protocol populations 	
 Difference between treatment groups in percentage of subjects that convert from non-dipper status at baseline to dipper status at end of sub-study¹

 To compare the percentage of subjects that convert from dipper status to non-dipper status between treatment groups in the ABPM ITT and ABPM per-protocol populations 	
 Difference between treatment groups in percentage of subjects that convert from dipper status at baseline to non-dipper status at end of sub-study¹

 To compare the effect of treatment with daprodustat to rhEPO on heart rate by ABPM in the ABPM ITT population 	
 Change from baseline to end of sub-study¹ in 24 hour average heart rate between treatment groups as measured by ABPM relative to time since administration of medication

1. The end of the sub-study is defined as Week 16, or Week 28 for subjects completing the sub-study prior to Amendment 2.

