12.12.4. Sample Size and Power Calculations

The sample size of this sub-study has been designed based on the primary sub-study objective to demonstrate superiority in average SBP change from baseline to end of sub-study between arms (daprodustat versus rhEPO), measured by ABPM over a 24 hour assessment period. Assuming a one-sided 2.5% significance level, a true standard deviation for SBP change from baseline measured by ABPM of 11 mmHg [Peixoto, 2000], and up to a 20% withdrawal rate from the sub-study, a sample size of 68 subjects per group (136 subjects in total) will provide greater than 80% power to detect a -6 mmHg difference in treatment groups (i.e., achieve superiority). Under these assumptions, superiority will be established if there is more than a 4.2 mmHg mean difference observed in favor of daprodustat.

Assuming a 40% screen failure rate for the additional ABPM entry criteria, approximately 228 subjects that are eligible for the main study will need to be screened for the sub-study in order to randomize approximately 136 subjects. See Section 9.2.3 for more information about sample size adjustments.

Unblinded ABPM data will be reviewed by the IDMC during the conduct of the trial as part of their data monitoring responsibilities. No formal interim analysis is planned.

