12.15.2.1. Summary of Changes

- Changes from country-specific Amendment 1 applied to global amendment
- Country-specific requirements for France and Czech Republic added.
- Section and appendix relating to darbepoetin alfa pre-filled syringe incidents, malfunctions and user errors. Section deleted as darbepoetin alfa pre-filled syringes are not subject to device reporting requirements.
- Time and events Table 7 ‘Schedule of Assessments Year 1 to End of Study’ modified. Main changes include new timepoints at Run-in (Week -4) and Week 2 for collection of information related to iron therapy; new timepoint at Week 52 for Kt/V_{urea} assessment; and transfusions and kidney transplant added to prompt completion of page in eCRF.
- Time and Events Table 8 ‘Schedule of Assessments for Patient Reported Outcomes, Genetics and Sub-studies’ modified. Main changes are changes to the ABPM sub-study assessments including prompts for the end of the 44hour ABPM assessments and prompts for recording the times the subject awakens and goes to sleep during this 44 hour ABPM period.
- Time and events Table 9 ‘Schedule of Assessments for Subjects Permanently Discontinuing Randomized Treatment’ modified. Main changes include IRT system call removed at all visits except Early Treatment Discontinuation Visit and End of Study Visit; new timepoints for collection of information related to iron therapy, transfusions; and kidney transplant added to prompt completion of page in eCRF.
- Text added to clarify those randomized to rhEPO who transition from HD to PD will change from epoetin alfa to darbepoetin alfa.
- Text relating to the timing of dialysis in relation to the study visit has been amended. The original text ‘For subjects receiving PD or home HD >3x/week, study visits must occur within 48 hours of their last dialysis session’ was inaccurate as PD is daily treatment.
- For the negatively adjudicated events in 200807, the reporting process has been updated and the investigator-reported term (not the adjudicator-reported term) will be used.
- In addition to allowing a historical (last 6 months) kidney ultrasound to be used to assess entry criteria, a provision was added for a more sensitive imaging study (e.g., MRI, CT) to be used to assess entry criteria.
- Other changes include minor wording changes for clarity, updating of section numbering and cross referencing, formatting changes (for consistency) and administrative changes.

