Protocol Activity (visits ± 1 week) (Note: All visit timings are relative to Day 1)	Screening					Day 1 through Week 208								Post- Week 52 through End of Study
	Week -8	Week -4	Day -21 ¹	Day -14 ¹	Day -12	Day 1	Week 4	Week 8 & 12	Week 16, 20 & 24	Week 28	Week 28 (End of week visit)	Week 52	Week 100, 148, 208	End of Study
Patient Global Impression of Severity (PGI-S) ⁵	X					X		X		X		X		
Patient Global Impression of Change (PGI-C) ⁵								X		X		X		
Short Form 36 (SF-36) ⁵						X		X		X		X		
EuroQol 5 Dimension 5 Level Health Utility Index (EQ-5D-5L) and EuroQol Visual Analogue Scale (EQ-VAS) ^{2, 5}						X		X		X		X	X	X

Section 7.1 Time and Events Table; Table 8 Schedule of Assessments for Patient Reported Outcomes, Genetics and Sub-studies; VEO assessments; new footnote added; footnote 5.

5 Subjects who are unable to or require assistance to read must not complete the questionnaires.

Section 7.1 Time and Events Table; Table 8 Schedule of Assessments for Patient Reported Outcomes, Genetics and Sub-studies; ABPM sub-study assessments. 44hr ABPM end, record awake and sleep times, and 44 urine collection prompts and timepoints added.

Protocol Activity (visits ±1 week) (Note: All visit timings are relative to Day 1)	Screening					Day 1 through Week 52							Post-Week 52 through End of Study	
	Week -8	Week -4	Day -21 ¹	Day -14 ¹	Day -12	Day 1	Week 4	Week 8 & 12	Week 16, 20 & 24	Week 28	Week 28 (End of week visit)	Week 52	Week 100, 148, 208	End of Study
ABPM sub-study(Appendix 12): Informed Consent		X												
Home BP monitoring(twice daily for PRIOR 4 consecutive days)			X				X	X	X	X				
44 hour ABPM start				X						X				
44 hour ABPM end					X						X			
Record awake and sleep times					X						X			
Pre- and post-dialysis weight				X ⁴										

Section 7.1 Time and Events Table; Table 8 Schedule of Assessments for Patient Reported Outcomes, Genetics and Sub-studies; footnote 4 removed

4. Additional to the timepoints specified in Table 7. Post dialysis weight to be measure, before the ABPM device is attached.

Section 7.1 Time and Events Table; Table 9 Schedule of Assessments for Subjects Permanently Discontinuing Randomized Treatment; IRT system call; IRT system call removed at all visits except Early Treatment Discontinuation Visit and End of Study Visit.

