$\geq 12^3$	Any change	Repeat Hgb and average values ⁶ ; if confirmed, temporary hold the dose and re-check Hgb at next study visit ¹ ; restart at one dose step lower when Hgb <11.5 g/dL and provided it has been at least 2 weeks from the prior study visit .

Section 12.6; Appendix 6: Randomized Treatment Dose Adjustment Scheme; footnote 1; last bullet point.

- For subjects ~~transitioning to dialysis~~ **changing dialysis modality from HD to PD:** Visits every 4 weeks for 12 weeks.

Section 12.6; Appendix 6: Randomized Treatment Dose Adjustment Scheme; footnote 2; word visit added for clarity.

2. This rule applies to any mandated **visit** or unscheduled visit, provided it has been at least 2 weeks from the prior study visit.

Appendix 11 Definition of Darbepoetin Alfa Pre-filled Syringe Incidents. Section deleted as darbepoetin alfa pre-filled syringes are not subject to device reporting requirements.

Definition:

- ~~Incident—Any malfunction or deterioration in the characteristics and/or performance of the pre-filled syringe, as well as any inadequacy in the labeling or the instructions for use which, directly or indirectly, might lead to or might have led to the death of a patient/user/other persons or to a serious deterioration in their state of health.~~
- ~~Not all incidents lead to death or serious deterioration in health. The non-occurrence of such a result might have been due to other fortunate circumstances or to the intervention of health care personnel.~~

It is sufficient that:

- ~~an **incident** associated with a pre-filled syringe happened and~~
- ~~the **incident** was such that, if it occurred again, might lead to death or a serious deterioration in health.~~

A serious deterioration in state of health can include:

- ~~life-threatening illness~~
- ~~permanent impairment of body function or permanent damage to a body structure~~

- a condition necessitating medical or surgical intervention to prevent one of the above
- fetal distress, fetal death or any congenital abnormality or birth defects

Examples of incidents

- a patient, user, care giver or professional is injured as a result of failure or misuse of the pre-filled syringe
- a patient's treatment is interrupted or compromised by failure of the pre-filled syringe
- a patient's health deteriorates due to failure of the pre-filled syringe

*Appendix 12; Section 12.12.3.3 Study Assessments; Week 28 Study Visit; sentence 3.
Wording change for clarity.*

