- Modified Time and Events Table 8 ‘Schedule for Assessments for Patient Reported Outcomes, Genetics and Sub-studies’ modified to add healthcare resource utilization data collection, to streamline ABPM assessments and to add timing for informed consent and additional eligible collection visits for PK sub-study.
- Modified Time and Events Table 9 “Schedule of Assessments for Subjects Permanently Discontinuing Randomized Treatment” to remove capture of rescue

- medications (rescue evaluation is triggered at on-treatment scheduled visits), to add healthcare resource utilization data collection, and to complete ABPM assessments.
- Added direction to see CEC Site Manual for full scope of reporting requirements.
 - Add clarifications for PD subjects as to how weight, blood pressure, and laboratory assessments are to be done.
 - Clarified timing of assessments relative to dialysis for SBP, DBP, HR and laboratory assessments.
 - Added reminder for the ordering of assessments for blood pressure and that the over-read of the Day 1 ECG is required to confirm eligibility.
 - Updated PRO section to add healthcare resource utilization data being collected for completeness and updated endpoint labels for EQ-5D-5L & EQ-VAS.
 - Revised statistical section to change from two-sided testing at the 5% level to one-sided testing at the 2.5% level; correct the comparator for the Null and Alternative hypotheses; to change significance levels to p-values; to add a more complete description of the adjustments to statistical model; to update hyporesponder analyses; and to add additional text regarding the interim analysis process.
 - Added exploratory endpoints around Hgb variability, iron parameters, transfusions, and dose adjustment scheme.
 - Edited Risk Assessment information to align with version 8 of the Investigator's Brochure.
 - Updated FSH level to confirm menopause.
 - Provision for possible adjustment to the Dose Adjustment Algorithm triggers for Hgb values 7.5 g/dL to <9.5 g//dL based on the review of blinded instream aggregate Hgb data.
 - Changes to ABPM sub-study to add atrial fibrillation/flutter screening, remove home BP monitoring, change from 44- to 24-hour APBM, change in time-point for assessment (from Week 28 to Week 16), and adjustments to objectives, endpoints and analysis.
 - Clarified additional inclusion and added additional eligible visits to collect PK samples in PK sub-studies.

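### The footnote that defines the ABPM endpoint time point cites Amendment 2, but Week 28 stayed the scheduled visit until Amendment 3

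*Protocol*

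**What the plan says.** The primary ABPM endpoint in Section 12.12.2 is "Change in 24 hour average SBP from baseline to end of sub-study", compared between treatment groups. The time point is not given in the endpoint itself. It comes from footnote 1, which also serves the other sub-study endpoints marked with it: "The end of the sub-study is defined as Week 16, or Week 28 for subjects completing the sub-study prior to Amendment 2".

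The other current text gives no second definition. Table 8, Table 9 and Sections 12.12.3.1, 12.12.3.3 and 12.12.3.4 describe a follow-up recording at Week 16 only. The analysis text in Section 12.12.5 refers to the end of the sub-study without naming a week, so it depends on the footnote.

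The change history in Appendix 15 shows when the schedule moved. The Amendment 3 summary (Section 12.15.3.1) lists, for this sub-study, "remove home BP monitoring, change from 44- to 24-hour APBM, change in time-point for assessment (from Week 28 to Week 16"). The Amendment 2 summary (Section 12.15.2.1) reports only "changes to the ABPM sub-study assessments including prompts for the end of the 44hour ABPM assessments" and prompts for recording sleep and wake times.

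**The concern.** The footnote is current text and cites an amendment by number. Its evident purpose is to accept Week 28 readings from subjects who finished under the old schedule. That works only if the amendment cited is the one that changed the schedule.

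If it is not, there is a group whom the rule sends to a visit at which they had no recording: subjects who completed the Week 28 recording while Amendment 2 was in force. Applied literally, their Week 28 value does not qualify and their Week 16 value does not exist.

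Two things would then be at stake for any such subject:

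- The primary sub-study comparison would lose an evaluable subject, and it has almost no margin above 80% power.
- The gap would count as missing data for a reason other than unwillingness or an un-evaluable reading. Section 12.12.5 uses the share of missing data due to those two reasons (more than 70%) to decide whether the primary analysis is considered sufficient or a control-based imputation may be added.

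Repairing the rule informally at analysis is also undesirable in a trial where sites know the treatment.

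**Working it through.** **Step 1. Which amendment moved the visit?** The amendment log is used here only to establish what the amendments did, since the live footnote cites one by number.

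- *Amendment 2, Table 8 as revised (Section 12.15.2.2):* the row "44 hour ABPM start" is marked at Day -14 and Week 28. Nothing is marked at Week 16.
- *Amendment 2, sub-study text (Section 12.15.2.2):* the edit is located at "Section 12.12.3.3 Study Assessments; Week 28 Study Visit; sentence 3", so the follow-up visit was still Week 28.
- *Amendment 3 (Section 12.15.3.1):* "change in time-point for assessment (from Week 28 to Week 16"). The front-matter summary of Amendment 3 lists the same change.
- *Amendment 3, list of specific changes (Section 12.15.3.2):* footnote 1 itself appears here, together with the replacement of Week 28 by the end-of-sub-study term.

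The switch therefore belongs to Amendment 3.

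**Step 2. Apply the footnote literally.**

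| Subject completed the sub-study | Recording scheduled at | Footnote assigns | Agree? |
|---|---|---|---|
| Before Amendment 2 | Week 28 | Week 28 | Yes |
| Under Amendment 2, before Amendment 3 | Week 28 | Week 16 | No |
| Under the Amendment 3 schedule | Week 16 | Week 16 | Yes |

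Only the middle row fails.

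**Step 3. Reproduce the plan's figures.** Inputs from Section 12.12.4: "Assuming a one-sided 2.5% significance level", SD 11 mmHg, difference 6 mmHg, 68 per group, up to 20% withdrawal.

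- Evaluable per arm: 68 × 0.80 = 54.4, taken as n = 54.
- Standard error of the difference: 11 × √(2/54) = 2.117 mmHg.
- Critical observed difference: t(0.975; 106 df) × SE = 1.983 × 2.117 = 4.20 mmHg. The plan states 4.2.
- Power: noncentral t with noncentrality 6/2.117 = 2.834, giving 80.2% (80.9% by the normal approximation). The plan states greater than 80%.

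The planned figures reproduce, and correcting the amendment number alters none of them.

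**Step 4. What if some subjects fall in the middle row?** The protocol does not give the number. The losses below are assumptions, starting at zero.

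| Evaluable lost per arm | n per arm | Critical difference (mmHg) | Power, t | Power, normal |
|---|---|---|---|---|
| 0 | 54 | 4.20 | 80.2% | 80.9% |
| 1 | 53 | 4.24 | 79.4% | 80.2% |
| 2 | 52 | 4.28 | 78.7% | 79.4% |
| 6 | 48 | 4.46 | 75.3% | 76.2% |

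For n = 52: SE = 11 × √(2/52) = 2.157; critical difference = 1.9835 × 2.157 = 4.28; noncentrality = 6/2.157 = 2.781. With two lost per arm, power is below 80% by either method.

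**The case against.** The best case on the other side has four parts.

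1. *The evidence is from the amendment log.* No other current section contradicts the footnote, and differences between a log and current text are not errors. The log's dates are also untidy: the front matter dates Amendment 3 as 2017-OCT-05, while Section 12.15.3 says Amendment 3 amends a version dated 2017-OCT-12. The untidy dates are real but do not matter here. The argument uses the order of the amendments and what each did, on which the front matter and Appendix 15 agree. The defect is in the live footnote, and the log is needed only to see what the cited amendment changed.

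2. *Nobody may be affected.* This stands. The text at hand does not give the date of Amendment 2 or of first sub-study enrolment, or the number who reached Week 28 between the two amendments.

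3. *The intent is obvious and the data would exist.* This stands in part. No section orders Week 28 readings to be discarded or set to missing, and further detail is left to the reporting and analysis plan, which is not at hand. A reader might infer that a group of subjects has no valid endpoint and that power has been lost. The documents do not support that. They show only that the definition, read literally, would not admit those subjects' readings.

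4. *It is a small matter.* This stands. The sub-study plans about 136 subjects in a trial of about 3000. Neither co-primary endpoint nor the superiority family is touched.

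**Conclusion.** Wrong as written; minor severity; sub-study only. The footnote that defines the ABPM endpoint time point names Amendment 2 where the protocol's own history points to Amendment 3, and no current section repairs it.

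The conclusion rests on reading the footnote literally and on the change history being right about which amendment moved the visit. The practical effect rests on a number the protocol does not give and may be nil, so the power losses under working are conditional illustrations. They do matter to this extent: the design has so little slack that excluding about two evaluable subjects per arm would break the stated greater-than-80% claim.

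**What to change.** In footnote 1 of Section 12.12.2, replace the reference to Amendment 2 with implementation of Amendment 3. Keep the exception tied to subjects completing the sub-study, and add in brackets that their end-of-sub-study ABPM was performed at Week 28. Make the derivation in the reporting and analysis plan match.

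Keep the rule tied to the recording actually performed. A rule based on the visit a subject was first scheduled for would reverse the fault: a subject enrolled under Amendment 2 and switched to a Week 16 recording when Amendment 3 took effect could be sent to Week 28, when no recording was made.

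The cost is one footnote and one derivation. Sample size, power, margin and analysis model do not change. The correction should be made before the ABPM data are analysed.
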